9.10 Poolability Analyses

Heterogeneity across sites and patient subgroups will be assessed with one-way analysis of variance. All poolability analyses will be performed on the FAS population. Treatment failures will be imputed with their baseline score. Missing data due to dropout will be imputed as last observation carried forward (LOCF).

If homogeneity is rejected, then an additional sensitivity analysis will be conducted based on a Bayesian hierarchical model (similar to a random effects model) with site and/or subgroup modeled as random effects, as appropriate.

Regardless of the result of the poolability analyses, data will be summarized by site and by subgroup.

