## 5.11 Number of Centers, Randomization and Allocation

Number of Centers participating: 22.

The subjects in the study will be randomized by site using variable block sizes.

The subjects in the study will stratified by extent of osteoarthritis, defined dichotomously by the Kellgren-Lawrence grade:

- Strata I: 0 & 1
- Strata II: 2 & 3

The study will recruit subjects in US and OUS sites.

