9.7 Covariate Analyses

Covariate analyses will be done on the PP population for the primary and secondary confirmatory endpoints by including each covariate of interest in an MMRM model, for both treatment groups, with one MMRM model per covariate listed below. Each covariate will appear in one MMRM.

The covariates are

- Age
- Gender
- BMI
- Lesion type (chondral or osteochondral)
- Number of lesions (single or multiple)
- Level of osteoarthritis (K/L score 0-1 or 2-3)
- Lesion size (total lesion size $\leq 3\text{cm}^2$ or $>3\text{cm}^2$)
- Previous ligament reconstruction (with or without)
- Meniscus status (intact, previous partial meniscectomy, concomitant meniscectomy)
- Activity status (active or inactive)

Note that the effect of interest is the Treatment x Covariate interaction term in the MMRM model, which will be tested using a 0.15 significance level.

Additionally, descriptive statistics will be provided by covariate level for categorical covariates.

For categorical covariates, we will perform an additional analysis, similar to the primary analysis, within each category of the covariate. From this analysis, the credible interval for the treatment effect will be reported for each category and assessed overlap.

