9.11 Poolability of Sites

The interaction between site and treatment on the poolability of KOOS will be compared using an ANOVA model. The model is

$$Y = \text{Site} + \text{Treatment} + (\text{Site} \times \text{Treatment})$$

Small sites with $n < 6$ will be combined into a single “other” site category.

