9.13 Poolability of Subgroups

The poolability of the patient subgroups will be assessed using the method described above. The following subgroups will be assessed (separately, with one ANOVA for each):

- HA type (to the extent that multiple HA types are used in the study)
- Unilateral vs Bilateral symptomatic knees
- Follow-up visits within the pre-COVID-19 specified window (24 Months Post- Procedure Visit ± 8 weeks) and Follow-up within the expanded window*, outside the initially specified window (24 Months Post- Procedure Visit $\pm 8-16$ weeks)
- On-site and off-site assessments of KOOS subscales**

* Following a pandemic coronavirus outbreak that occurred in Q1, 2020 the time window of follow-up visits were extended in the following manner:

- a. Six (6) months post-procedure ± 12 weeks (instead of ± 4 weeks)
- b. Twelve (12), Eighteen (18), Twenty-four (24) months post-procedure ± 16 weeks (instead of ± 8 weeks)
- c. Annual post 24 months visits ± 16 weeks, until last patient reaches 24 months, (instead of current ± 8 weeks)

** * Following a pandemic coronavirus outbreak that occurred in Q1, 2020 Subject off-site completion of the following Self-reported Questionnaires:

- a. KOOS subscales
- b. Tegner score
- c. SF-12 Health Survey (v2)

- d. 2000 IKDC Subjective Knee Evaluation Form

10 Missing Data

10.1 Within a KOOS Subscale Score:

Treatment of missing data within a KOOS scale measure:

1. KOOS Subscale Score:

As per KOOS scale guideline, subscale scores will be computed based on observed items only if not more than 2 items are missing. Where more than two items are missing, the KOOS subscale score will be scored missing.

2. Overall KOOS Score:

Overall KOOS Score will be defined as the average over the KOOS subscales, if not more than two subscales are missing. Where more than two KOOS subscales are missing, the Overall KOOS score will be scored missing.

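### The hierarchical site model in SAP 9.10 runs only if a low-power homogeneity test rejects; it should be run in every case and carried into the Month-60 plan

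*SAP*

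**What the plan says.** SAP 9.10 sets the rule: "If homogeneity is rejected, then an additional sensitivity analysis will be conducted based on a Bayesian hierarchical model", with site and/or subgroup as random effects. It does not say whether the treatment effect itself is to be random across sites. What is produced whatever the test shows is descriptive: "Regardless of the result of the poolability analyses, data will be summarized by site and by subgroup".

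For sites, SAP 9.11 names the test: "The interaction between site and treatment on the poolability of KOOS will be compared using an ANOVA model", with terms for site, treatment and their product. It adds: "Small sites with $n < 6$ will be combined into a single “other” site category". SAP 9.10 itself speaks of a one-way analysis of variance, which has no interaction term. SAP 9.12 tests region (US or outside the US) by treatment. SAP 9.13 adds further factors, including the pandemic-related visit windows and "On-site and off-site assessments of KOOS subscales".

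SAP 9.10 to 9.13 give no significance level. SAP 9.7 gives one for covariate interactions, "which will be tested using a 0.15 significance level", and Protocol 10.11 uses the same level for poolability at Month 60. Protocol 10.11 has no hierarchical follow-up, and site appears neither there nor in the covariate list of Protocol 10.9.

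**The concern.** The model that allows for variation between sites is most useful when such variation exists, and the plan fits it only if a test has already detected that variation. With few subjects per site the test often will not detect it. The report would then hold a non-significant interaction, by-site descriptive tables and the pooled result. It would have no estimate of how much the effect varies between sites and no overall effect that carries that variation.

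The pandemic factors raise a similar point. If few subjects completed the KOOS off-site or fell in the extended window, a non-significant interaction says little, and SAP 9.13 plans no interval on the difference in effect that would show how little.

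**Working it through.** **The plan's own figures.** The documents give no power for the poolability tests. The nearest stated figures are in Protocol 10.7.1 for the primary endpoint (120 vs 59, SD 25, one-sided 0.025). A noncentral-t calculation gives 93.5% at a difference of 13.9 (stated 93.5%), 80.0% at 11.2 (stated 80%) and 99.99% at 22.5 (stated 99%). They reproduce.

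**Inputs.**
- Sites: "Number of Centers participating: 22" (Protocol 5.11); up to 30 in SAP 3.
- Subjects: up to 251 (Protocol 5.10); full analysis set 160 + 79 = 239 (Protocol 10.7.1); 250 to 500 in SAP 1.1; Month-60 planning size 120 + 59 = 179 (Protocol 10.7.1).
- Allocation 2:1, randomized by site in blocks of 3 and 6 (SAP 6).
- Level: not stated, so 0.05 and 0.15 are both shown.
- Assumption, not in the documents: the true treatment effect varies across sites with SD tau = 0.5 residual SD. That is 0.5 × 20.9 = 10.45 KOOS points on the Month-24 SD, or 0.5 × 23 = 11.5 on the SD in SAP 8.

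**Formula, equal sites.** With J sites and N subjects, each site has h = n1·n2/(n1 + n2) = (2/9)·(N/J). Under random effects the interaction F statistic is distributed as (1 + h·0.5²) times a central F on J − 1 and N − 2J degrees of freedom. So the miss probability is P(F ≤ Fcrit/(1 + 0.25h)).

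**N = 251, J = 22.** h = (2/9) × 11.41 = 2.535, factor 1.634, degrees of freedom 21 and 207.
- Level 0.05: Fcrit = 1.607; 1.607/1.634 = 0.984; miss = 51.5%.
- Level 0.15: Fcrit = 1.345; 1.345/1.634 = 0.823; miss = 31.0%.

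**Range.**

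| N | Sites | Miss at 0.05 | Miss at 0.15 |
|---|---|---|---|
| 251 | 22 | 51% | 31% |
| 239 | 22 | 54% | 33% |
| 251 | 30 | 59% | 37% |
| 179 | 22 | 67% | 45% |
| 500 | 22 | 16% | 7% |
| 500 | 30 | 21% | 9% |

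With tau = 0.3 residual SD, N = 251 and 22 sites, the misses are 83% and 64%.

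**Uneven sites and merging.** A simulation (2,000 runs per setting, blocks of 3 and 6, uneven site sizes, sites under six subjects merged, N = 251, 22 sites) gives misses of 49-53% at 0.05 and 30-32% at 0.15. The null rejection rate at 0.05 is 4.9%. Merging therefore changes little.

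**Two-category factors (region, window, completion mode).** With share q in one category, the standard error of the difference in effect is SD × sqrt[(4.5/N)·(1/q + 1/(1 − q))]. At N = 239 a difference of 0.5 SD is missed as follows. Category sizes are not in the documents, so the splits are assumptions.

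| Split | Miss at 0.05 | Miss at 0.15 |
|---|---|---|
| 50/50 | 56% | 35% |
| 20/80 | 69% | 49% |
| 10/90 | 81% | 63% |

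**Width of the sensitivity interval.** With 22 equal sites, SE = sqrt(SE0² + tau²/22).
- Month 24: SE0 = 20.9 × sqrt(1/160 + 1/79) = 2.87. With tau = 10.45 the SE is 3.64, about 27% larger.
- Month 60: SE0 = 25 × sqrt(1/120 + 1/59) = 3.98. With tau = 10.45 it is 4.56, and with tau = 0.5 × 25 = 12.5 it is 4.79, so about 15-20% larger.

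**The case against.** A reader might infer that pooling itself rests on a non-significant test. The documents do not say that. SAP 9.3 and Protocol 10.5 specify the pooled primary analysis on the full analysis set without any such condition, and the test decides only whether a sensitivity analysis is added.

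A reader might also infer that allowing for site variation could overturn superiority. The planning figures do not support this. At the protocol's pessimistic Month-60 difference of 13.9, the ratio to the wider standard error is 13.9/4.79 = 2.90 or 13.9/4.56 = 3.05. At the reported Month-24 difference of 22.5 it is 22.5/3.64 = 6.2. All lie well above 1.96.

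Other objections stand in part:
- **Level.** The only interaction level in the documents is 0.15, where the miss rate is about a third, not a half. But SAP 9.10 to 9.13 do not adopt it, so what counts as rejection is undefined.
- **Assumed spread.** Nothing in the documents shows a 0.5-SD spread. If site effects were independent of control means, the Agili-C SD would be expected near sqrt(20.9² + 10.45²) = 23.4, and it was 20.1. This is not proof of homogeneity, since site effects could be negatively correlated with control means, but it is no sign of large variation either. The standard-error calculation also treats the observed SD as residual SD.
- **Target of inference.** The hypotheses compare mean improvement between arms and name no population of sites. This is a good reason to keep the random-site model as a sensitivity analysis.
- **Existing output.** By-site summaries are unconditional and region by treatment is tested. Neither gives an overall effect that carries between-site variation.
- **Timing.** Protocol 10.7.1 already reports Month-24 results, so the SAP analysis has probably been run. The change matters most for Month 60.

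**Conclusion.** The point holds as a weakness in the sensitivity analysis, not as a flaw in the primary analysis. If the rule is followed as written, the hierarchical model would be skipped about 51% of the time (level 0.05) or 31% (level 0.15) when the effect truly varies between sites by half a residual SD, with 251 subjects and 22 sites. On the Month-60 planning size of 179 the same test would miss it 67% or 45% of the time. At 500 subjects and 22 sites the rates drop to 16% and 7%, but the protocol has at most 251.

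These rates rest on the assumed spread and, in the formula, on equal sites; uneven sites and merging hardly move them. The level has to be assumed because the SAP states none. For Month 60, Protocol 10.11 has no hierarchical follow-up at all, so the gap there does not depend on any test result.

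**What to change.** In SAP 9.10, delete the opening conditional clause and fit the hierarchical sensitivity model in every case. State that it has random site and random site-by-treatment effects. Report the average treatment effect, its posterior probability of superiority, and the between-site SD of the effect with a 95% credible interval.

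For region, visit window and on-site versus off-site KOOS completion, report the difference in treatment effect with a 95% interval. Keep the tests as descriptive, state their level, and reconcile the one-way analysis of variance in SAP 9.10 with the interaction model in 9.11.

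Add the same sensitivity analysis, with site named, to Protocol 10.11 for Month 60. If the Month-24 analysis is complete, label any rerun there as added afterwards.

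The cost is a wording change, one model that the SAP already names, and a sensitivity interval that will usually be somewhat wider than the primary one. The primary analysis does not change.

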9.11 Poolability of Sites

The interaction between site and treatment on the poolability of KOOS will be compared using an ANOVA model. The model is

$$Y = \text{Site} + \text{Treatment} + (\text{Site} \times \text{Treatment})$$

Small sites with $n < 6$ will be combined into a single “other” site category.

9.12 Poolability of Geographical Regions

The interaction between region (U.S. and OUS) and treatment on the poolability of KOOS will be compared using an ANOVA model.

9.13 Poolability of Subgroups

The poolability of the patient subgroups will be assessed using the method described above. The following subgroups will be assessed (separately, with one ANOVA for each):

- HA type (to the extent that multiple HA types are used in the study)
- Unilateral vs Bilateral symptomatic knees
- Follow-up visits within the pre-COVID-19 specified window (24 Months Post- Procedure Visit ± 8 weeks) and Follow-up within the expanded window*, outside the initially specified window (24 Months Post- Procedure Visit $\pm 8-16$ weeks)
- On-site and off-site assessments of KOOS subscales**

* Following a pandemic coronavirus outbreak that occurred in Q1, 2020 the time window of follow-up visits were extended in the following manner:

- a. Six (6) months post-procedure ± 12 weeks (instead of ± 4 weeks)
- b. Twelve (12), Eighteen (18), Twenty-four (24) months post-procedure ± 16 weeks (instead of ± 8 weeks)
- c. Annual post 24 months visits ± 16 weeks, until last patient reaches 24 months, (instead of current ± 8 weeks)

** * Following a pandemic coronavirus outbreak that occurred in Q1, 2020 Subject off-site completion of the following Self-reported Questionnaires:

- a. KOOS subscales
- b. Tegner score
- c. SF-12 Health Survey (v2)

- d. 2000 IKDC Subjective Knee Evaluation Form

10 Missing Data

10.1 Within a KOOS Subscale Score:

Treatment of missing data within a KOOS scale measure:

1. KOOS Subscale Score:

As per KOOS scale guideline, subscale scores will be computed based on observed items only if not more than 2 items are missing. Where more than two items are missing, the KOOS subscale score will be scored missing.

2. Overall KOOS Score:

Overall KOOS Score will be defined as the average over the KOOS subscales, if not more than two subscales are missing. Where more than two KOOS subscales are missing, the Overall KOOS score will be scored missing.

10.2 Primary Analysis

At the primary (final) analysis, all subjects will have completed full follow-up time. Treatment failures will have their outcome replaced with their baseline value. If some subjects drop out and missing data is present after performing the steps mentioned above (if necessary), any remaining missing data will be handled through multiple imputation, however only weakly informative priors will be used for this final analysis, as follows:

$$\alpha_t \sim N(0, 1) \text{ for } t = 6, 12, 18 \text{ months}$$

$$\lambda_t^2 \sim IG(0.5, 312) \text{ for } t = 6, 12, 18 \text{ months}$$

$$\tau^2 \sim IG(0.5, 312)$$

See the adaptive design report in appendix 1 for full details of the model, as well as the informative prior distributions to be used at the interims.

10.3 Confirmatory Secondary Analyses

Missing data for the confirmatory secondary endpoints at the final analysis will be handled in a manner similar to the primary analysis. Treatment failures will have their outcome replaced with their baseline value. If necessary, we will next perform the steps for missing information with the KOOS subscale and overall KOOS score as described above. If missing data is still present due to subject drop out, the missing data will be handled through multiple imputation, using only weakly informative priors as in described above.

For Secondary Confirmatory Endpoint IV, the analysis method will differ slightly due to the dichotomous nature of the data. Treatment failures and dropouts will be imputed as described above for the continuous change from baseline endpoint. After imputation, the outcomes will be dichotomized for the purpose of testing the responder rate hypothesis.

10.4 Other Analyses

Additional secondary and safety data will not be subject to any imputation and will be summarized on an observed case basis.

10.5 Missing Data as a Result of the Coronavirus Outbreak

As described in ‘FDA Guidance on Conduct of Clinical Trials of Medical Products during COVID-19 Pandemic Guidance for Industry, Investigators, and Institutional Review Boards’, March 2020, ‘FDA recognizes that the COVID-19 pandemic may impact the conduct of clinical trials of medical products... FDA recognizes that protocol modifications may be required, and that there may be unavoidable protocol deviations due to COVID-19 illness and/or COVID-19 control measures’.

As of March 15, 2020, several sites have notified CartiHeal that on-site subjects follow-up visits are suspended, and that the ability to perform follow-up imaging (x-ray and MRI) is limited.

In order to ensure adequate oversight and minimize loss to follow-up of subjects, the following changes were applied:

1. Expansion of the follow-up visit windows to:
 - a. Six (6) months post-procedure \pm 12 weeks (instead of the \pm 4 weeks)
 - b. Twelve (12), Eighteen (18), Twenty-four (24) months post-procedure \pm 16 weeks (instead of \pm 8 weeks)
 - c. Annual post 24 months visits \pm 16 weeks, until last patient reaches 24 months, (instead of \pm 8 weeks)

Subject off-site completion of Self-reported Questionnaires:

- a. KOOS subscales
- b. Tegner score
- c. SF-12 Health Survey (v2)
- d. 2000 IKDC Subjective Knee Evaluation Form

3. Virtual visits (telephone)/web to record medications, AEs and SAEs

4. Updates to the monitoring plan to allow for remote rather than in-person monitoring during the pandemic-related restrictions.

In case of missing data, despite the proactive measures that describe above, the rules that were described in 10.1-10.4 will be applied.
